 - a. VFD to day 28 is defined as the number of days of unassisted breathing to day 28 after randomization, assuming a patient survives for at least two consecutive calendar days after initiating unassisted breathing and remains free of assisted breathing. If a patient returns to assisted breathing and subsequently achieves unassisted breathing prior to day 28, VFD will be counted from the end of the last period of assisted breathing to day 28 unless a period of assisted breathing was less than 24 hours and the purpose of assisted breathing was a surgical procedure.
 - b. If the patient is receiving assisted ventilation at day 28 or dies prior to day 28, VFD will be 0.
 - c. Any VFDs before patients are placed on comfort care will be counted.
 - d. Unassisted breathing is defined as the patient breathing spontaneously with a face mask, nasal prong oxygen, or on room air, T-tube breathing, tracheostomy mask breathing, or CPAP < 5 without pressure-support or intermittent mandatory ventilation, or with the use of noninvasive ventilation solely for sleep-disordered breathing. Assisted breathing is defined as any level of ventilatory support at pressures higher than the unassisted breathing thresholds.
2. Secondary endpoints will include the following:
 - a. All-cause 28-day mortality.
 - b. The number ICU-free days to day 28 after enrollment
 - c. The occurrence of complications of treatment (specifically pneumothorax, ventilator-associated pneumonia, hypotension requiring pressors, pneumatocele).

IRB Protocol: _____

Site PI: _____

Version Date: 2/9/2020

Page 12 of 34

- d. Percentage of patients discharged to extended care facilities, on mechanical ventilation, or to in-patient or home hospice.
- e. Newly requiring continuous oxygen therapy at discharge

Recruitment process

Research personnel (e.g., study physicians, research coordinators, research assistants) will seek out the senior treating physician for patients meeting study inclusion criteria to request permission to seek consent from the patient or, if the patient cannot participate in the consent process, from the patient's legally recognized representative (LAR) or proxy decision maker for participation in the study. If the senior treating physician agrees, the research personnel will pursue obtaining consent.

Informed consent process

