In the event that research personnel or the treating physician believes the patient is not competent, either because of the condition requiring treatment (e.g., traumatic brain injury) or the medications being used to treat anxiety or pain (e.g., sedatives and/or narcotics) consent will be sought from the patient's legally authorized representative (LAR). All subjects for whom LAR or proxy consent is obtained will be asked to provide consent if decisional capacity is regained and will be given the opportunity to withdraw from the study if they do not give consent to continue participating. If decisional capacity is not regained on or before day 28, re-consent is not required. If decisional capacity is regained on or before day 28 and the patient is still hospitalized, they will be re-consented as soon as decisional capacity is regained.

The consent form specifically states that the patients do not have to decide whether they want to participate at the point in time when consent is being discussed. It also states that the patients are free to consider the decision and/or to discuss it with others in private, without any study personnel or physicians involved in their care being present. The consent form also notes, however, that the patient must decide whether they wish to participate before they have been receiving mechanical ventilation for 24 hours as receiving ventilation for longer than 24 hours is one of the exclusion criteria.

The proposed study will be conducted in eight states in the U.S. Each site may have different local or regional regulations regarding who can serve as a LAR and when an LAR is considered necessary. The consent form specific to each site will be modified to include the regulations regarding LARs for each site prior to submitting it for individual IRB approval.

If a patient is deemed incompetent or cannot otherwise participate in the consent process the same process described for seeking consent from the patient will be used to seek consent from the LAR.

Patient Follow-up Process

Research personnel will see patients enrolled in the study daily until day 28 or until the patient is discharged from the ICU, either to another floor in the hospital or home. If a patient is transferred to a progressive care or step-down unit and continues to receive ventilation, the patient will be followed on a daily basis until the patient is extubated or dies or until day 28.

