If the patient is discharged from the ICU before day 28 and is no longer receiving mechanical ventilation, research personnel will review medical records and/or contact the patient on day 28 (or the Friday before or Monday after if day 28 occurs on a weekend) to determine if the patient is still alive, discharged from the hospital (and if so, when), and whether the patient has experienced any adverse events (see the risk management and emergency response section) between the day the patient was discharged from the ICU and day 28.

IRB Protocol: _____

Site PI: _____

Version Date: 2/9/2020

Page 14 of 34

If a patient is extubated and reintubated before day 28, the patient will continue to receive ventilation according to the group to which the patient was originally randomized.

If a patient is randomized to receive sigh breaths and is transported to the operating room, CT, IR or other hospital department after randomization, the patient should be ventilated according to usual practice, i.e., they need not continue to receive sigh breaths during the time they are away from the ICU. Sigh breaths should be restarted on their return.

Data collection

1. Assessment on enrollment

- a. Demographics (age, gender, self-reported race)
- b. Pregnancy test (serum or urine) for women of child-bearing potential (this is part of usual care and does not represent a study-related expense)
- c. Co-existing medical conditions
- d. Evidence of previous thoracic surgery
- e. Height, weight, BMI and calculated predicted body weight
- f. Date and time of injury
- g. Date and time of admission to ED
- h. Date and time patient was admitted to ICU
- i. Description of any operations done between ED and ICU admission
- j. Blood alcohol level (if recorded)
- k. Smoking status
- l. Initial BP in ED
- m. Initial Glasgow Coma Scale in ED

2. Initial assessment

- a. Date and time patient was intubated and started on invasive mechanical ventilation
- b. Ventilator used, ventilator mode, tidal volume, F_1O_2 , PEEP, peak and plateau pressures, whether prone positioning was utilized
- c. The latest arterial blood gas prior to the ventilator settings recorded, indicating pH, the $PaCO_2$, the PaO_2 , the HCO_3 , the F_1O_2 , the SaO_2 and the PEEP level and the time the sample was obtained
- d. If the patient has been randomized to sigh ventilation:
 - i. Is the patient's BMI > 35 ?
 - ii. If yes, is the P_{plat} for the sigh breath $40 \text{ cmH}_2\text{O}$?

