Mortality will be analyzed separately as a secondary endpoint. ICU-free days (up to day 28, with deaths prior to day 28 classified as having ICU28 = 0) will be analyzed as just described for VFD28. Occurrences of complications of treatment (adverse effects) prior to day 28 will be analyzed using logistic regression.

Interim Analyses; Early Termination

A Data and Safety Monitoring Board (DSMB) will be appointed to oversee the progress of the SiVent trial and to review adverse events and efficacy. The DSMB will be comprised of 3 members: one pulmonary physician, a surgeon who treats ARDS, and a statistician. The members will be independent of the institutions where the clinical sites are located. The DSMB will meet approximately every 6 months (alternately in-person and by conference call). The DCC will prepare a complete summary of data on recruitment, adherence to protocol, protocol violations, withdrawal rates, adverse events, deaths, and the primary and secondary outcomes. One of the responsibilities of the DSMB at each of its meetings is to make recommendations concerning continuation, revision, or termination of the clinical trial. Here we describe guidelines for interim analysis of results, with the goal of providing 'stopping boundaries' for the primary outcome (VFD28).

Our expectation is that three formal interim analyses will be conducted: the first when approximately 1/3 of the total patients have been evaluated, the second when about 2/3 have been evaluated, and the third when all patients have been evaluated. The monitoring boundaries for these 'looks' at the data are based on the Lan-DeMets 'alpha spending function' approach. This yields an overall significance level of approximately 0.05. We have chosen monitoring boundaries in the 'Pocock' family [Pocock S (1977), Group sequential methods in the design and analysis of clinical trials. *Biometrika* 64: 191-199]. The software is 'Id98', an interactive program based on the research of K.K. Gordon Lan and David DeMets:

[<https://www.biostat.wisc.edu/content/lan-demets-method-statistical-programs-clinical-trials>]

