Each patient will be seen daily by research personnel from the time each patient is enrolled until day 28 or until the patient is discharged from the ICU, either to another floor in the hospital or home or dies. If a patient is transferred to a progressive care or step-down unit and continues to receive ventilation, the patient will be followed on a daily basis until the patient is extubated or dies or until day 28.

These daily visits will seek evidence of adverse events or complications per the study manual of procedure. If adverse events or complications have occurred they will be recorded on the adverse event case report form. Whether a patient experiencing an adverse event continues on the study or is withdrawn will be decided by the treating physician.

If the patient is discharged from the ICU before day 28 and is no longer receiving mechanical ventilation, research personnel will review medical records and/or contact

IRB Protocol: _____

Site PI: _____

Version Date: 2/9/2020

Page 26 of 34

the patient on day 28 to determine whether the patient has experienced any adverse events between the day the patient was discharged from the ICU and day 28.

The investigator will report all adverse events to the DCC within 24 hours of their occurrence. The local Institutional Review Board (IRB) will also be informed in a timely manner. The investigator will then submit a detailed, written report to the DCC and to the IRB no later than five days after the investigator discovers the event.

The DCC will report all serious, unexpected and study-related adverse events to the DSMB by fax or telephone within seven calendar days. A written report will be sent to the DSMB within 15 calendar days and these reports will be sent to investigators for submission to their respective IRBs. The DSMB will also review all adverse events during each scheduled interim analysis. The DCC will distribute the written summary of the DSMB's periodic review of adverse events to investigators for submission to their respective IRBs.

All patients in this study will be hospitalized in an intensive care unit. Accordingly, emergency care will be readily available at all times. The cost of treatment for all study-related adverse events will be covered by each individual hospital.

Potential benefits

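### Complications are counted to day 28, but once a patient is out of the ICU and off the ventilator the plan relies on a single unstructured look-back, which can bias the comparison if ICU time differs between arms

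*Combined protocol and SAP*

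**What the plan says.** Endpoints, item 2c, lists complications of treatment as a secondary endpoint, "specifically pneumothorax, ventilator-associated pneumonia, hypotension requiring pressors, pneumatocele". The Data Analysis section of the Statistical plan gives the method: "Occurrences of complications of treatment (adverse effects) prior to day 28 will be analyzed using logistic regression". It says nothing about exposure time or about how closely patients were observed.

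The Patient Follow-up Process section sets the intensity of observation: "Research personnel will see patients enrolled in the study daily until day 28 or until the patient is discharged from the ICU". There is an extension for patients who move to progressive care or step-down while still ventilated: "the patient will be followed on a daily basis until the patient is extubated or dies or until day 28". Surveillance and reporting adds: "These daily visits will seek evidence of adverse events or complications per the study manual of procedure". The Daily Assessments list under Data collection has specific items for vasopressors, pneumothorax or pneumatocele, BAL results and complications including pneumonia.

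For a patient who is out of the ICU and off the ventilator before day 28, "research personnel will review medical records and/or contact the patient on day 28". That check covers "any adverse events (see the risk management and emergency response section) between the day the patient was discharged from the ICU and day 28". The Closeout assessments include discharge diagnosis codes and procedure codes, but no item for the four complications.

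**The concern.** The endpoint window is the same length in both arms, but the chance of detecting an event within it is not constant. It changes when the patient leaves the ICU off the ventilator. Ventilator-free days are the primary endpoint and ICU-free days a secondary one, so the trial itself treats the time of that change as something the intervention may shift.

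If the sigh arm leaves sooner, more of its 28 days rest on the weaker check, and events missed there lower its observed complication rate. If sighs prolong ICU stay, the bias reverses. Pneumothorax and pneumatocele are most exposed: they can arise after ventilation ends, and a patient contacted on day 28 cannot be relied on to report a small one. They also bear directly on baro- or volutrauma, the first foreseeable risk in the Risk/Benefits Assessment, where the protocol says it found no human studies of sighs given in a similar fashion.

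**Working it through.** The documents give no complication rate, ward hazard, detection rate or ICU-day difference, so there is no stated figure to reproduce. The calculation below is illustrative.

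**Inputs**
- Control mean of 15 ventilator-free days, SD 9.9, 544 patients, 80% power, 1% withdrawal: Sample size estimate.
- 272 per arm: assumes 1:1 allocation, which is not stated.
- Sigh-arm gain of 2.4 days: no target difference is stated. The figures above imply (1.96 + 0.842) × 9.9 × √(2/269.3) = 2.39.
- Assumed: 20% mortality, 4 ICU days after weaning, 21-day hospital stay, ICU hazard 1% per day in both arms.
- Assumed: ward hazard r times the ICU hazard, with r = 0.1, 0.5 or 1; ward detection d = 50%.

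**ICU days among survivors.** Deaths score 0, so mean ventilator days in survivors = 28 − VFD/(1 − mortality).
- Control: 28 − 15/0.8 = 9.25; plus 4 gives about 13.3 ICU days.
- Sigh: 28 − 17.4/0.8 = 6.25; plus 4 gives about 10.3 ICU days.

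The difference is 3 days. At 10% mortality it would be 11.33 − 8.67 = 2.7 days.

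**Observed risk** = 1 − exp{−[0.01 T + 0.01 r d (21 − T)]}, where T is ICU days. The artefact is the between-arm difference at d = 0.5 minus the difference at d = 1. For r = 0.5 and d = 0.5:
- Control exponent: 0.133 + 0.0025 × 7.7 = 0.15225, risk 14.12%.
- Sigh exponent: 0.103 + 0.0025 × 10.7 = 0.12975, risk 12.17%.

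| r | Difference, full detection (real) | Difference, 50% detection | Artefact | Odds ratio, full → 50% |
|---|---|---|---|---|
| 0.1 | 2.38 points | 2.52 points | 0.14 | 0.80 → 0.78 |
| 0.5 | 1.27 points | 1.95 points | 0.68 | 0.91 → 0.84 |
| 1.0 | 0 | 1.27 points | 1.27 | 1.00 → 0.91 |

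The standard error of the difference, √[p₁(1−p₁)/272 + p₂(1−p₂)/272], is 2.7 to 3.1 points at 50% detection.

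**Sensitivity.** A second model runs to day 28 with 14 control ICU days, hazards of 1% to 2% per day, and 50% to 80% detection.
- Equal ICU and ward hazard: the artefact is 0.4 to 1.5 points for a 2-day ICU difference and 0.7 to 3.2 points for 4 days. Two-sided 5% rejection with no true difference becomes 5.1% to 6.7% and 5.5% to 12.3% respectively.
- Ward hazard one tenth of the ICU hazard: the artefact is 0.04 to 0.4 points, against a real difference of 1.6 to 5.5 points from shorter ICU exposure.

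In both models the artefact is zero if ICU time is equal or detection is complete.

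**The case against.** A reader might infer that the arm leaving sooner must show fewer complications by construction. The documents do not support that. The day-28 check looks back over the whole interval since ICU discharge, so the window is not cut short. A false deficit needs an ICU-time difference, events after ICU discharge and imperfect detection, all together. Nor does daily follow-up simply end at ICU discharge, since ventilated step-down patients keep it.

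A reader might also take every odds ratio below 1 in such a model as bias. At full detection with half the ward hazard, 0.91 reflects fewer days at the higher ICU hazard; it is a real effect. Assuming that nothing is detected on the ward would contradict the check the plan provides.

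Other routes could catch ward events. Closeout diagnosis and procedure codes are not limited to ICU patients. Investigators must report adverse events to the coordinating center within 24 hours. Radiology reports are kept in the patient file, though the text does not say they extend past the ICU. The Manual of Procedures, not available here, may contain a structured day-28 form. Ventilator-associated pneumonia is tied to ventilation, and pressor-requiring hypotension is, as a matter of judgment, mostly an ICU event. Harm is also monitored through the lower boundary for ventilator-free days and the DSMB's adverse event reviews.

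All of this stands, and it limits the likely size. It does not close the gap: none of these routes is tied to the four-item endpoint in the text, and the day-28 rule still allows patient contact alone.

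**Conclusion.** The concern holds as a possible differential ascertainment bias on one secondary safety endpoint. Its direction would favor the arm with the shorter ICU stay, and pneumothorax and pneumatocele would carry most of it. Its size cannot be calculated from the documents. Under the main assumptions (1% daily ICU hazard, 3-day ICU difference, 50% ward detection, ward hazard one tenth of to equal to the ICU hazard) it is about 0.1 to 1.3 percentage points, less than half a standard error. The sensitivity model reaches 3.2 points only with a 4-day difference, 50% detection and a 2% daily hazard undiminished on the ward.

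The reason to act is interpretive: with the data as planned, fewer complications in the arm leaving sooner could not be separated into a real exposure effect and missed events.

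A smaller gap lies in the timing of the check. Patient Follow-up Process allows "or the Friday before or Monday after if day 28 occurs on a weekend", so a Friday check leaves the last one or two days uncovered. Surveillance and reporting states day 28 without that window.

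**What to change.** In Patient Follow-up Process and in Surveillance and reporting, replace the choice between record review and patient contact with a required review of the available hospital record, including imaging reports, through hospital discharge or day 28 for every patient. Use the same four-complication list as the endpoint, with onset dates, and make patient contact an addition. State the timing window identically in both sections.

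In Data Analysis, add a supportive description: complications by arm, split by onset before or after ICU discharge or the end of ventilation, with exposure time by arm. This separates real exposure effects from possible missed events without replacing the planned logistic regression.

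An analysis confined to a short early window, such as the first week, need not be required. Under the assumptions above with 10% to 20% mortality, sigh-arm survivors average about 6 to 9 ventilator days, so many could leave close observation within that window, and later events would be discarded.

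The cost is modest chart-review time for existing research personnel, one closeout item and one descriptive table. Treatment does not change.
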